Randomized, double-blind prospective trial to test the efficacy and acceptability of therapeutic, antiseptic mouth rinses to inactivate SARS-CoV-2 virus in saliva of SARS-CoV-2+ patients 18-65 years of age. All mouthrinses are commercially available Colgate products and will be used according to on-label instructions. Patients will be randomized to a mouthrinse and will be asked to give a saliva sample immediately before and after a 30-60 second mouthwash. Saliva samples will be collected from patients at 15-minute intervals thereafter up to one hour (15, 30, 45 and 60 min). The samples will be stored and used for RT-PCR detection of SARS-CoV-2 virus and viral infectivity assays, along with quantitative cytokine and chemokine concentration (pg/mL, Luminex). Patients will also complete a short survey on the taste and experience of using the mouthwash. Peripheral blood will be collected at the end of salivary collection. Participants, except controls, will be provided materials and oral hygiene instruction related to daily use of oral hygiene products provided by the study. In the seven-day period between study visits, participants will be directed to brush with Colgate toothpaste (at least twice per day) and rinse with the Colgate mouthrinse (according to on-label procedures). Controls are not given Colgate products and will be asked to carry out their typical oral hygiene regimen with the products they typically use. All participants will be asked to keep a daily diary of oral hygiene performance, product usage, COVID-19 symptoms and exposures. Daily diary data confirms compliance with oral hygiene protocol, and is needed for data inclusion and analysis, as it relates to secondary and tertiary outcomes for visit 2. Participants will be scheduled to return to the GoHealth Clinical Research Unit at one week after the baseline assessment, during which additional salivary (1 time point, 2 mL of saliva over 5 min, no rinse will occur) and blood samples will be collected. At the conclusion of sample collection, the participant will undergo a periodontal exam. Study participation concludes following the periodontal exam at the end of the second on site study visit. Patients with any periodontitis or gingivitis diagnosis will be informed of their diagnosis and will be referred to an oral healthcare provider for further treatment. Patients' final periodontal status will be a tertiary outcome of the periodontal exam and will be reported as the percentage of participants categorized into each diagnostic group; patients with a periodontal diagnosis will be informed of the findings and will be referred to an oral healthcare provider for further treatment. Participants who provide salivary and blood samples and follow study protocols will receive a \$30 gift card as compensation at the end of visit 1 and \$50 at the end of visit 2. This study involves two 90-minute visits.

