3. STUDY DESIGN

One of the aims of this placebo-controlled, randomized, double-blinded study is to measure the efficacy of antiseptic mouthwashes on reducing SARS-CoV-2 cellular infectivity in COVID+ patient saliva (described above). Asymptomatic and symptomatic SARS-CoV-2+ subjects will be enrolled in the study (according to Inclusion and Exclusion Criteria - Section A.3). Symptomatic SARS-CoV-2+ subjects will be enrolled within 7 days of symptom onset. Subjects' samples are collected in the GoHealth Clinic (Adams School of Dentistry, UNC Chapel Hill, North Carolina, USA). Asymptomatic SARS-CoV-2+ subjects will be enrolled within one week of likely exposure. Study participants who meet all inclusion criteria without any exclusion criteria will be randomized to either an experimental or control group using block randomization.

Participants give a baseline salivary sample (2 mL over 5 min) and then asked to rinse with an mouth rinse for 30-60 sec (on-label instructions) according to the table below:

mouthrinse*	Number of final participants (sample size)	Group
1.5% w/v hydrogen peroxide rinse (Peroxyl)	25**	Experimental
0.12% Chlorhexidine Gluconate (Periogard)	25	Experimental

1 st Peroxyl; 2 nd Periogard [^]	25	Experimental
0.075% Cetylpyridinium Chloride (Colgate Total Zero)	25	Experimental
Sterile Water	25	Control

**All mouthrinses are commercially available in the USA, routinely used in clinical settings, and will be used in an on-label manner.*

***30 participants will be enrolled per regimen to ensure that complete data will be obtained from at least 25 participants per regimen. We assume that ≤ 5 enrollees will drop out or have incomplete data. 30 participants will be enrolled per arm to collect full data sets from 25 participants per arm, assuming some patients will need to be replaced due to inability to complete a visit (missing data).*

[^]For the sequential Peroxyl (1st) and Periogard (2nd) rinses, both oral rinses will be conducted in an on-label fashion. The patient will begin by rinsing with 10 mL of Peroxyl for 60 sec and then expectorate the mouthrinse into an empty tube. Then the patient will rinse with 15 mL of Periogard for 30 seconds and spit this mouthrinse into another empty tube.

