At the conclusion of sample collection, the participant will undergo a periodontal exam and will receive a \$50 gift card for their participation in visit 2. Study participation concludes following the periodontal exam after visit 2.

Missing data may occur due to participants being unable to complete a study visit due to health concerns or insufficient salivary production. Any missing data will be excluded from the study analysis. We do not anticipate that this will bias the data in any way. To accommodate this eventuality, we plan to enroll 30 participants per arm, to be able to have 25 participants per arm with full datasets.

All salivary samples will be collected on ice in sterile 50 mL conical vials and blood will be collected in EDTA-containing blood collection tubes. All collection tubes will be labelled “COVID Core” using pre-printed labels including the participants random alphanumeric study ID. Saliva samples will be cataloged and stored at the UNC Delta COVID Translational Initiative (also referred to as the COVID Core) for future RT-PCR, cytokine and chemokine concentration (Luminex) and viral infectivity assays. Samples will be transported on ice in a secondary container from the collection site to 4403A Koury Hall in leak proof biohazard bags. Samples will be processed according to the **sample processing and outcomes** procedure (below).

Participants who successfully provide salivary and blood samples and follow study protocols will receive a \$30 gift card as compensation at the end of visit 1 and \$50 at the end of visit 2. This study involves two, 90 minute on site visits.

During the period that the study participants are present in the clinic and giving saliva samples, we will monitor patient wellbeing and inquire about their comfort. If participants exhibit signs of distress or if oxygen saturation drops, research study staff will contact emergency medical responders to visit the patient and if deemed appropriate, the participants will be escorted to UNC hospital (adjacent building).

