5.4 Adherence Assessment

Adherence would be defined as rinsing with the mouthrinse for 30-60 sec (as directed on the label) before expectorating, and then providing saliva samples at 15 min time points and a blood sample.

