6.2.5 Completion/Final Evaluation

This study requires two 90 minute visits. Participation is completed after the 2nd visit. For the second visit, participants will be scheduled to return to the GoHealth Clinical Research Unit at one week after the baseline assessment, during which additional salivary (1 time point, 2 mL of saliva over 5 min, no rinse will occur) and blood samples will be collected. At the conclusion of sample collection, the participant will undergo a periodontal exam and will receive a \$50 gift card for their participation in visit 2. Study participation concludes after visit 2 with no additional follow-up, as results are not relevant to the patient's clinical course and treatment management.

Subjects may withdraw from the trial at any time at their own request, or they may be withdrawn at any time at the discretion of the Investigator or Sponsor for safety, behavioral or administrative reasons.

The Investigator may discontinue a subject if, in the opinion of the Investigator, the subject is no longer a suitable candidate for the study. Possible reasons for the discontinuation of a subject are including but not limited to: adverse event, protocol deviation, insufficient saliva production, missed appointment, or subject no longer meets the eligibility criteria. The reason for discontinuation will be documented in the CDART record.

Patients may be removed from the study due to an allergic reaction to a mouth rinse or due to failure or inability to comply with study procedures.

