If a patient suffers from xerostomia/dry mouth, such that s/he cannot produce the baseline salivary sample volume or the immediate, 15 minute and 30 minute post-rinse saliva volumes, s/he will be removed from the study with a parking voucher, but without a visit 1 \$30 gift card and will be replaced. This would lead to missing data at the uncompleted time points. If a patient suffers from dry mouth, such that s/he cannot produce salivary sample volumes needed for later time points (45 min or 60 min post-rinse) but s/he produced sufficient baseline, immediate, 15 min and 30 min post-rinse samples, the participant will still be compensated with the visit 1 \$30 gift card and parking vouchers, and will remain in the study for visit 2 participation, if willing. At the conclusion of the visit 2 on site appointment (after saliva and blood samples have been collected and the periodontal exam is completed), participants will receive a \$50 gift card and parking vouchers. If a participant fails to carry out the at-home oral hygiene regimen with diary, cannot provide salivary or blood samples at visit 2, or cannot undergo the oral exam, they will not be provided the \$50 gift card for visit 2. Missing or deficient samples will be noted in CDART.

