9. INTERVENTION DISCONTINUATION

Subjects may withdraw from the trial at any time at their own request, or they may be withdrawn at any time at the discretion of the Investigator or Sponsor for safety, behavioral or administrative reasons.

The Investigator may discontinue a subject if, in the opinion of the Investigator, the subject is no longer a suitable candidate for the study. Possible reasons for the discontinuation of a subject are including but not limited to: adverse event, protocol deviation, insufficient saliva production, missed appointment, failure to comply with oral hygiene regimen, subject no longer meets the eligibility criteria. The reason for discontinuation will be documented in the patient's CDART record.

Patients may be removed from the study due to an allergic reaction to a mouth rinse or due to failure or inability to comply with study procedures. If a patient suffers from xerostomia/dry mouth, such that s/he cannot produce the baseline salivary sample volume or the immediate, 15 minute and 30 minute post-rinse saliva volumes, s/he will be removed from the study with a parking voucher, but without a visit 1 \$30 gift card and will be replaced. If a participant suffers from dry mouth, such that they cannot produce salivary sample volumes needed for later time points (45 min or 60 min post-rinse) but produced sufficient baseline, immediate, 15 min and 30 min post-rinse samples, s/he will still be compensated with the visit 1 \$30 gift card and parking vouchers, and will remain in the study for visit 2 participation, if willing.

At the conclusion of the visit 2 appointment (after saliva and blood samples have been collected and the periodontal exam is completed), participants will receive a \$50 gift card and parking vouchers. If a participant fails to carry out the at-home oral hygiene regimen with diary, cannot provide salivary or blood samples at visit 2, or cannot undergo the oral exam, s/he will not be provided the \$50 gift card for visit 2. Missing or deficient samples will be noted in CDART.

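### Visit 2 data can be excluded for poor home compliance, with no cut-off or analysis set, and the exclusion can fall more on the product arms than on controls

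*Combined protocol and SAP*

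**What the plan says.** **Inclusion rule.** The Précis (Design and Outcomes) states: "Daily diary data confirms compliance with oral hygiene protocol, and is needed for data inclusion and analysis". The sentence goes on to limit this to secondary and tertiary outcomes at visit 2.

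**Regimens.** In the same paragraph, participants in the product arms are told to brush with Colgate toothpaste at least twice a day and to rinse with the Colgate mouthrinse as labelled. For the control arm: "Controls are not given Colgate products and will be asked to carry out their typical oral hygiene regimen with the products they typically use". All arms keep the diary.

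**Removal.** Section 9 lists, among possible reasons for discontinuation, "failure to comply with oral hygiene regimen, subject no longer meets the eligibility criteria". Sections 6.2.5 and 9 both list protocol deviation and allow removal "due to failure or inability to comply with study procedures".

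**Payment.** Sections 6.2.5 and 9 also address non-compliance at home: "If a participant fails to carry out the at-home oral hygiene regimen with diary". The only consequence given there is loss of the $50 visit 2 gift card. Neither section says whether the data are kept.

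**Missing data.** Section 3: "Any missing data will be excluded from the study analysis. We do not anticipate that this will bias the data in any way".

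**Definitions.** Section 5.4 covers the clinic visit only: "Adherence would be defined as rinsing with the mouthrinse for 30-60 sec", followed by the saliva and blood samples. Section 10.3, on populations, restates eligibility.

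**Comparison at stake.** Section 10.5.2 expects lower cytokine and chemokine levels in Colgate users than in non-intervention controls. Section 10.6 tests changes from baseline by repeated measures regression and names no analysis set.

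**The concern.** Compliance with the home regimen happens after randomisation. If it decides whose visit 2 data are used, the groups compared are no longer the randomised groups. That matters most when the condition is harder to meet in some arms than in others, as it is here: four arms have a product regimen that can be failed, and the fifth continues as usual.

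Participants have an acute infection, and the adverse-effect table in Section 2.2 lists irritation and altered taste for some of the rinses. Illness and irritation are plausible reasons to stop rinsing, and both could also move inflammatory markers. Those excluded may therefore differ from those kept on the outcome itself.

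There are two routes to exclusion. A participant may be sampled at visit 2 and then left out because of the diary. Or the participant may be discontinued before visit 2 and become missing data, which Section 3 treats as harmless. Because no threshold is set, two analysts could build different visit 2 data sets from the same text. Section 10.5 adds that the committee evaluating the data is not masked to group, which is a further reason to settle the rule in advance.

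**Working it through.** **Step 1: can the exclusion differ between arms?**

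| Way to be excluded | Product arms | Control arm |
|---|---|---|
| No diary returned | Yes | Yes |
| Prescribed product regimen not followed | Yes | No such regimen, according to the Précis |
| Discretionary removal (Sections 6.2.5, 9) | Yes | Yes, but with no product regimen to fail |

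The control exception is explicit only in the Précis. The term non-intervention controls in Section 10.5.2 supports it. The Précis paragraph on interventions and duration, and Sections 2.2, 3 and 5.1, describe home products or hygiene instruction without repeating the exception.

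**Step 2: the plan's own allowance.** Section 3 enrols 30 per arm to obtain 25 complete, assuming that at most five "enrollees will drop out or have incomplete data". That is 5/30 = 16.7%, and 30 × (1 − 5/30) = 25, so the figure reproduces. It covers loss from all causes and is not a compliance rate. I use it only as an upper scenario.

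**Step 3: bias.** The documents give no non-compliance rate and no link between compliance and cytokines, so everything below is assumed:
- a share p of would-be non-compliers in every arm, p = 10% or 16.7%;
- all of them excluded from product arms and none from control;
- no true effect;
- non-compliers' change from baseline differing from that of others by d = 0.5 or 1.0 SD of change.

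Measured from the compliers' mean, the product arms average 0 and the control arm averages p × d. The size of the bias in an arm-versus-control difference is therefore p × d:
- 0.10 × 0.5 = 0.05
- 0.10 × 1.0 = 0.10
- 0.167 × 0.5 = 0.08
- 0.167 × 1.0 = 0.17

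If half of the would-be non-compliers in the control arm are also excluded, the bias is d × (p/2)/(1 − p/2). This runs from 0.5 × 0.05/0.95 = 0.03 to 1.0 × 0.083/0.917 = 0.09. If non-compliers are higher at both visits but change as others do, d = 0 and the bias is zero.

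**Step 4: effect on a false positive.** Simulation with five arms of 25, change score with total SD 1, one marker, Tukey–Kramer over five arms at two-sided 0.05, 40,000 runs per setting. The table gives the chance that at least one product arm is significantly lower than control when no product has an effect. With no exclusion it is 1.1%.

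| p, d | Non-compliers rise more | Non-compliers rise less |
|---|---|---|
| 10%, 0.5 | 1.9% | 0.7% |
| 10%, 1.0 | 3.2% | 0.4% |
| 16.7%, 0.5 | 2.7% | 0.5% |
| 16.7%, 1.0 | 5.5% | 0.2% |

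For one given product arm the figure is 0.3% with no exclusion and at most 1.7%. With half of the non-complying controls also excluded, the range when non-compliers rise more is 1.4–3.0%. The false discovery rate step across markers is not modelled and would lower these figures.

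**The case against.** **The rule may mean only that a diary was returned.** Grammatically, it is the diary data that are needed, and all arms keep a diary. On that reading the Précis rule binds every arm alike. This is a fair reading. But the same sentence gives confirming compliance as the diary's purpose, and Section 9 separately lists regimen failure as a reason for discontinuation, which a returned diary does not prevent.

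**Controls can be excluded too.** A reader might infer that controls cannot breach the rule at all. The documents do not support that. Controls are asked to keep to their typical routine, must complete the diary, and come under the payment clause, which applies to any participant. What stands is a difference in degree: only the product arms have a prescribed product regimen to fail.

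**The plan has a mitigation.** In Section 5.1 staff monitor diary adherence and contact participants between visits. This may reduce non-compliance, but it sets no threshold and does not say what happens to the data of those who still fail.

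**Regimen failure looks like a payment matter.** Section 6.2.5 removes and replaces participants for insufficient visit 1 saliva, but attaches only loss of the gift card to regimen failure. The Section 9 item is permissive and is missing from the parallel list in 6.2.5. This lowers the likelihood of removal without ruling it out.

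**An effect in users is a legitimate aim.** The hypothesis speaks of participants using Colgate products. That could justify a supportive compliers analysis. It does not justify selecting on compliance in some randomised arms and comparing the result with an arm not selected in the same way.

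**The effect is small and the outcome secondary.** Both are correct. The trial is sized on paired infectivity comparisons, and Section 10 calls the analyte comparison descriptive, although Section 10.6 tests it.

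**Conclusion.** The point holds as a concern about the visit 2 secondary and tertiary data, chiefly the cytokine comparison. As written, the plan permits exclusion after randomisation that can fall more on the product arms, with no cut-off and no analysis set to limit it.

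A reader might infer that the rule favours the products. The documents do not show this. If non-compliers' markers rise more (worsening illness, irritation), excluding them flatters the products. If they rise less (recovery), excluding them works against the products. Under the assumptions above the bias is about 0.05–0.17 SD of change in either direction, smaller if controls are also excluded, and zero if non-compliers change as others do. Only the most extreme corner takes the chance of a false finding of lower levels above 5%. None of the rates or differences comes from the documents.

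Nor does the point reach the primary result: visit 1 infectivity and viral load do not depend on the home week. It is worth correcting because the correction is cheap, not because the likely distortion is large.

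**What to change.** 1. Replace the inclusion condition in the Précis, and state the same set in Section 10.3: *Visit 2 secondary and tertiary data are analysed for all randomised participants with a visit 2 sample or exam, in the assigned arm, whatever the diary shows.*
2. In Section 9, strike the first of the two reasons in "failure to comply with oral hygiene regimen, subject no longer meets the eligibility criteria". State there and in Section 6.2.5 that non-compliance with the home regimen or diary is not a reason to withdraw anyone before visit 2 sampling, including under the headings of protocol deviation or failure to comply with procedures.
3. Report diary-recorded adherence and visit 2 missingness by arm.
4. If a compliers-only analysis is wanted, label it supportive and fix its cut-off before unblinding.

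The gift-card rule can stay. Visit 2 samples and diaries are already planned, so no new data or participants are needed. The cost is in what is estimated: the result becomes the effect of being assigned the products, which may be smaller than the effect in full compliers.

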
Interventions and Duration

Subjects will have a brief oral exam and will be asked to rinse with an unlabeled/blinded antiviral mouth rinse for 30-60 sec and provide 2 mL of saliva prior to the rinse and 2 mL of saliva

immediately post-rinse, 15 min post-rinse, 30 min post-rinse, 45 min post-rinse, and 60 min post-rinse. Subjects will also be asked to complete a short survey about the rinsing experience. A blood sample will be taken. Subjects will be onsite for a 90 min initial visit appointment. Patients will be sent home with Colgate toothpaste and mouthrinse for a daily oral health regimen, where participants will brush and rinse twice daily and maintain a take-home diary on their oral care regimen and COVID-19 symptoms. Patients will return for a second visit one week later for a salivary sample, blood draw and periodontal exam.

Sample Size and Population

We will enroll 30 outpatient SARS-CoV-2+ subjects per mouth rinse, (to achieve a total of 25 subjects with full data sets per mouth rinse,) with 5 mouth rinses, requiring us to enroll 125 SARS-CoV-2+ patients. Patients will be randomized to their mouthrinse. These patients will have already had a confirmed SARS-CoV-2+ test prior to enrollment. There will be no stratification to our randomization. In addition to having a SARS-CoV-2+ test, patients will need to be at least 18 y.o.a. and at most 65 y.o.a. and in fair oral health without any known allergies or reactions to commercial dental products or mouthrinses. Patients who are pregnant, nursing/lactating, have a cognitive or developmental disability, have kidney dysfunction, have an active oral herpes flare up, have any oral viral infection and/or flare up, have significant mucosal tears, growths or damage to their mouth, have uncontrolled severe periodontal disease with bleeding gums, or those with severe xerostomia will be excluded from the study. There are no exclusion criteria based on gender or race.

Table of Abbreviations and Definition of Terms

Abbreviation / Term	Definition	Additional details or range of value
baseline	Refers to the blood and saliva sample collection time point prior to mouth rinse use at study visit 1.	
BOP	Bleeding on probing- sites where the gingiva/gum bleeds after probing	0 not bleeding; 1 bleeding
CDART	Carolina Data Acquisition and Reporting Tool	0mm to 20mm, recession plus probing depth
CAL	Clinical attachment level	Probing depth plus recession (mm)
Co-I	Co-investigator	

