10.4 Study Stopping Rules

Analysis will occur at several points, while enrolling and collecting samples from 125 patients, in batches of 25 randomized participants. Analysis will occur after enrollment of 25, 50, 100 and then 125 participants and will include viral load and replication (as measured by changes in genomic, strand, and subgenomic expression and will be evaluated and compared between treatment groups). No interim analyses of data will be performed. mRNA obtained from salivary samples will be analyzed and will be assessed by RT-PCR at time points 0 and 30 min. Infectivity assays will be subsequently performed on salivary samples collected at time points 0 min ('baseline') and 30 min post rinse with cycle threshold of 22 or lower (CT22) as determined by RT-PCR using primers specific for SARS-CoV-2 viral products. If the cycle threshold is above 22 (CT22), samples are considered to contain insufficient virus for use in viral infectivity assays. This cycle threshold has been empirically determined by the [name] laboratory (personal communication, [name]).

If saliva samples from patients 6-7 days post-diagnosis are found to routinely have insufficient viral load at interim analysis (at n=25 or 50), the study will be modified for more stringent enrollment criteria (with inclusion up to 5 days post-diagnosis rather than 7, as salivary viral load diminishes with time after infection). Because all oral rinse products are commercially available, low risk products that have previously undergone extensive safety testing and approval procedures, we do not anticipate a situation where safety concerns to participants necessitates halting the study. Adverse events will be reported and reviewed by our internal quality control committee. Medical problems that occur in our facility will be reported as needed to the IRB board and emergency medical personnel will be contacted to care for the patient and potentially bring them to the adjacent UNC medical hospital. If a significant number of adverse events or reactions are witnessed (defined as more than 1 per 20 patients), a safety review will be triggered and study personnel will look at the records in an unblinded fashion to see if one mouthrinse is causing reactions. If that is the case, the mouthrinse study arm associated with adverse events will be discontinued, but the mouthrinse arms associated with minimal adverse events will continue.

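### The stated enrolment total of 125 contradicts the plan's own 30 per rinse across five rinses, which is 150; 125 is the number of complete data sets

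*Combined protocol and SAP*

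**What the plan says.** The Précis, under Sample Size and Population, states "We will enroll 30 outpatient SARS-CoV-2+ subjects per mouth rinse", aims for 25 complete data sets per rinse, and ends the same sentence "with 5 mouth rinses, requiring us to enroll 125 SARS-CoV-2+ patients".

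Section 3 (Study Design) supports the per-arm figure in two places. The note under the table of arms says "30 participants will be enrolled per arm to collect full data sets from 25 participants per arm". It explains the margin by the need to replace people who miss a visit, and allows for at most 5 losses per regimen. The table itself shows 25 final participants in each of five arms, sterile water included. The later paragraph on missing data says "we plan to enroll 30 participants per arm, to be able to have 25 participants per arm with full datasets".

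Section 10.4 (Study Stopping Rules) supports the other figure. It places analyses "while enrolling and collecting samples from 125 patients" and has them carried out batch by batch, each batch being 25 people. It then says "Analysis will occur after enrollment of 25, 50, 100 and then 125 participants".

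No section prints 150.

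**The concern.** One sentence applies the same verb to 30 per rinse and to 125 overall, and with five rinses these disagree. Section 10.4 repeats 125 as an enrolment figure, so correcting the Précis alone would leave the conflict in place.

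The number has practical use. Section 6.2.3 has the randomisation schedule prepared before enrolment starts, and the documents do not give its length. A schedule built for 125 holds 25 per arm and has no room for the 5 extra per arm that the plan adds against loss. Anyone deciding when to close recruitment, or when the last batch in Section 10.4 is due, would also have to choose between the two figures.

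**Working it through.** **Inputs**
- Enrolled per arm: 30 (Précis; Section 3, twice).
- Complete per arm: 25 (Précis; Section 3).
- Arms: 5, being four active and one sterile water (Section 3 table).
- Allowance for loss: up to 5 of 30 per arm, 5/30 = 16.7% (Section 3, table note).
- Stated total to enrol: 125 (Précis; Section 10.4).
- Required per arm: about 25, from a paired t-test with d = 0.7 and Bonferroni correction over four comparisons (Section 10.2, Sample Size and Randomization; Section 10.6).

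**Can 125 be reproduced as an enrolment total?**
- Arms × enrolled per arm: 5 × 30 = 150. No.
- Active arms only: 4 × 30 = 120. No.
- Arms × complete per arm: 5 × 25 = 125. Yes, but this counts complete data sets.
- Cross-check from completers back to enrolment: 125 / (1 − 5/30) = 150.

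**Size of the gap**
- 150 − 125 = 25 participants; 25/150 = 16.7%.
- Position of the last count in Section 10.4: 125/150 = 83.3% of the enrolment implied per arm.

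**If 125 were a ceiling, with no replacement beyond it**

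Enrolled per arm = 125/5 = 25. Complete = enrolled × (1 − loss).

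| Loss | Complete, total | Complete, per arm |
|---|---|---|
| 5% (assumed) | 118.75 | 23.75 |
| 10% (assumed) | 112.5 | 22.5 |
| 5 in 30 (plan's allowance) | 104.2 | 20.8 |

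For comparison, 150 × 25/30 = 125 complete, or 25 per arm.

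**What that would mean for power, on the plan's own basis**

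Paired t-test, d = 0.7, α = 0.05/4 = 0.0125. The plan does not state sidedness; two-sided is assumed. Power comes from the noncentral t distribution with n − 1 degrees of freedom and noncentrality d√n.
- n = 25: noncentrality 0.7 × √25 = 3.50, power 78.0%. Power of 80% needs n = 26, so the plan's figure of about 25 is reproduced closely as an analysable number per arm.
- n = 21: noncentrality 3.21, power 67.7%.
- n = 20: noncentrality 3.13, power 64.6%.

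**The case against.** The strongest reply is that the intended total is easy to infer. Thirty per arm appears in the Précis and twice in Section 3. Sections 6.2.5 and 9 say that participants who cannot give the required early saliva samples will be replaced, and Section 11.3.3 provides for recording this. On that view 125 is a slip and the trial would still reach 25 complete per arm. The point about intent stands, and so does the point about replacement: a shortfall arises only if 125 is enforced as a ceiling. Neither makes 125 correct as an enrolment total, and its use in Section 10.4 means it is not a single slip.

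The shortfall figures count complete two-visit data sets. The rinse samples for the primary outcome are all taken at visit 1, so someone lost before visit 2 may still contribute primary data. This limit also stands: 20.8 per arm is not a forecast of the number in the primary analysis.

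A reader might also infer that the final efficacy analysis is scheduled before enrolment ends. The documents do not support that. Section 10.4 describes batch analyses and never calls the one at 125 final, and Sections 10.5 and 10.5.1 place the laboratory outcomes weeks to months after the visits. Nor are the counts in Section 10.4 unlabelled: they are expressly enrolment counts. The difficulty is that their end point equals the completer total.

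**Conclusion.** The total to enrol is wrong as written. On the plan's own figures it is 150 for 125 complete data sets, a difference of 25 participants (16.7% of 150), and the same error runs through Section 10.4. This follows from the printed numbers by multiplication and needs no outside assumption.

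The consequences are conditional. About 104 complete data sets, and power near 65–68% instead of 78%, require that enrolment stops at 125, that no replacement goes beyond it, that 5 in 30 are lost, and that those losses also remove primary data. The documents do not show that this would happen, so the point should not be read as a finding that the trial is underpowered. It is an inconsistency in a governing number that should be corrected before the randomisation schedule is fixed.

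**What to change.** 1. In the Précis, state 150 enrolled (30 per arm) to obtain 125 complete (25 per arm).
2. In Section 10.4, either extend the enrolment counts to 150 or restate 125 as complete data sets, and reword the phrase about collecting samples to match. These are different time points. A complete data set needs visit 2 a week after visit 1, so the last completions follow the last enrolment; and because Section 3 allows for 5 or fewer losses per arm, 125 complete could also be reached before 150 are enrolled.
3. Prepare the randomisation schedule for at least 150.
4. Have the sponsor state whether replacements under Sections 6.2.5, 9 and 11.3.3 count within the 150 or are added to it. The Section 3 table note suggests within, but Sections 6.2.5 and 9 set no cap. Counting them within 150 would leave an arm short of 25 if it lost more than 5.

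In the protocol this is a change of text: one number, the counts in Section 10.4 and one sentence on replacement. It adds no participants to the 30 per arm already planned, unless the sponsor chooses to add replacements on top. The documents do not show which total was approved or budgeted; if that was 125, those records would need to be brought into line.
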